6.5 POOLING OF CENTRES

This section is not applicable.

6.6 HANDLING OF MISSING DATA AND OUTLIERS

6.6.1 Safety data and other data

In general, missing data will not be imputed and all reasonable efforts will be taken during the study conduct to obtain such data. Only observed values will be analysed. Data of subjects who withdrew after the screening examination or were not treated will be only listed.

6.6.2 AE dates and times

Missing or incomplete AE dates will be imputed according to BI standards (see DM&SM “Handling of missing and incomplete AE dates”). [3]

6.6.3 Missing plasma concentrations and pharmacokinetic parameters

Missing data and outliers of PK data are handled according to BI standards (see “Standards and processes for analyses performed within Clinical Pharmacokinetics/Pharmacodynamics”) [2].

6.7 BASELINE, TIME WINDOWS AND CALCULATED VISITS

In general, baseline values will be the measurements taken most recently prior to the first administration of study drug. If this value is not available, the measurement at screening visit will be used. If the lab is repeated at screening, then the last one should be used.

For efficacy analyses, baseline is defined as the pre-treatment observation at C1V1. If C1V1 is missing, then Screening will be used for baseline.

Visit will be labelled according to the flow chart in the protocol: Study day will be calculated relative to the date of the first administration of study drug. The day prior to first administration of study drug will be 'Day -1' and the day of first administration of study drug will be 'Day 1'; therefore 'Day 0' will not be used.

Clinical disease status will be assessed at screening and at the start of each new cycle (e.g., before Cycle 2, 3, 4 and 5, etc.) as well as EOT.

While nominal times listed in this section should be adhered to as closely as possible, the actual sampling times will be recorded and used for determination of pharmacokinetic parameters.

7. PLANNED ANALYSIS

For all the analyses in this open label phase I trial, patients will be included in the dose cohorts they were originally assigned to.

Tabulations of frequencies for categorical data will include all possible categories and will display the number of observations in a category as well as the percentage (%) relative to the respective treatment group. The category “missing” will be displayed where applicable (i.e., if and only if there are actually missing values in the data).

For in-text tables, the set of summary statistics is: N (number of patients with non-missing values), mean, standard deviation (SD), median, Q1 (lower quartile), Q3 (upper quartile), depending on the data.

For end-of-text tables, the set of summary statistics is: N/Mean/SD/Q1/Median/Q3. For appendix tables, the set of summary statistics is: N/Mean/SD/Min/Q1/Median/Q3/Max.

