3.2 DISCUSSION OF TRIAL DESIGN, INCLUDING THE CHOICE OF CONTROL GROUP(S)

The primary objective of this trial is to determine the MTD. The most important secondary objective is to assess the safety of BI 836909 given as continuous intravenous infusion.

For the first 4 doses up to and including 1.6µg/d dose cohorts single patient cohorts have been chosen since no clinical benefit is expected at these low doses.

For the remaining dose cohorts a standard 3+3 design has been chosen as this is an established standard approach in phase I studies in oncology:

The following dose cohorts will be tested as single patient cohorts: 0.2, 0.4, 0.8 and 1.6 µg/day.

If a patient has been on treatment in one of the above-mentioned dose cohorts for 2 weeks without DLT the first patient of the next higher dose cohort will be entered. In case that a DLT has been observed in the single patient cohorts 5 additional patients will be entered on this actual dose level.

Intra-patient dose escalation is allowed once to the next higher dose within the first 4 above-mentioned dose cohorts up to 1.6µg/d.

In case that no DLTs have been observed during the first cycle within the single patient dose cohorts the patient can be treated at the next higher dose level in subsequent cycles. Only one

Proprietary confidential information.

© 2018 Boehringer Ingelheim International GmbH or one or more of its affiliated companies. All rights reserved.

This document may not - in full or in part - be passed on, reproduced, published or otherwise used without prior written permission.

intra-patient dose escalation step is allowed. This approach of intra-patient dose escalation reduces the number of patients treated at pharmacologically inactive doses to a minimum and increases the likelihood of treatment benefit for patients entered at low dose.

Prior to treatment of a patient at the next higher cohort a safety committee quorum needs to be obtained to oversee the observation period of this dose level to make sure that no additional patients must be entered at that dose level and that a patient can be entered at the next higher dose level. If the safety committee recommends treatment of additional patients at the lower dose level 2 additional patients must be entered at the lower dose level first. The 3 + 3 design will then be followed.

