4.1.4.3 Dose reductions and dose delays

Related SAEs/AEs of \geq grade 2 or non-drug related SAEs/AEs of \geq grade 2 deemed intolerable by the patient or the treating physician and not responding to appropriate medical management will result in a pause until resolution to baseline or grade 1. A pause of a maximum duration of 14 days and a dose reduction to the next lower dose level is allowed if clinically indicated. Only one dose de-escalation step is allowed.

DLT events in any cycle, cases meeting the pre-defined hepatic injury criteria (ref. [5.2.2.1](#)) and infusion related reactions or cytokine release syndromes \geq grade 3 will lead to permanent discontinuation in the dose escalation phases. After recovery to baseline or grade 1 continuation of the cycle at the next lower dose tier is allowed. Only one dose de-escalation step is allowed.

CNS events \geq grade 2 irrespective of relatedness that have not resolved to baseline or grade 1 within one week despite treatment interruption will lead to permanent discontinuation in the dose escalation phase. CNS events that have resolved to baseline or grade 1 within one week can be continued at the next lower dose level. Only one dose de-escalation step is allowed.

In case of dose reductions all future courses will also be at the reduced dose level.

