7.3.1 Primary endpoint analyses

[figure not shown]
In order to identify the MTD, the number of patients with DLTs during the first course at each dose level will be displayed descriptively by dose level.

In addition, the number of patients with all DLTs during any treatment course will be analysed. Analysis of other adverse events and laboratory parameters is described in [Section 7.3.4](#).

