7.3.5 Pharmacokinetic analyses

The secondary pharmacokinetic endpoint C_{ss} [REDACTED] will be descriptively explored, and if possible, dose proportionality will also be explored descriptively. Attainment of steady state will be determined by visual examination of the data.

Refer to [Section 5.5.1](#) for pharmacokinetic parameters to be calculated. The derivation of the parameters will be according to sponsor’s standard operating procedures.

All evaluable patients will be included in the pharmacokinetic analysis. Patients who are considered as not evaluable will be listed with their individual plasma concentrations and individual pharmacokinetic parameters, however, will not be included in descriptive statistics for plasma concentrations, pharmacokinetic parameters or other statistical assessment. A patient is considered not evaluable if the subject has an important protocol violation relevant to the evaluation of pharmacokinetics or has insufficient data.

Proprietary confidential information.

[figure not shown]
© 2018 Boehringer Ingelheim International GmbH or one or more of its affiliated companies. All rights reserved.

This document may not - in full or in part - be passed on, reproduced, published or otherwise used without prior written permission.

Concentrations will be used for graphs and calculations in the format that is reported in the bioanalytical report. Only concentrations within the validated concentration range will be used for the calculation of pharmacokinetic parameters. Plasma concentrations will be plotted graphically versus time for all subjects as listed in the drug plasma concentration-time tables. For the presentation of the mean profiles, the geometric and arithmetic mean and the planned blood sampling times will be used. If the actual sampling time deviates significantly from the planned time, the corresponding plasma concentration will be excluded from the calculation of descriptive statistics.

Pharmacokinetic analyses of the plasma concentration-time data will be performed using a validated software program (e.g., Phoenix Winnonlin) and for this purpose the actual sampling time for pre-dose samples will be set to zero.

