6. GENERAL ANALYSIS DEFINITIONS

6.1 TREATMENTS

Patients are administered BI 836909 as a continuous 4-week infusion followed by a 2-week break for 5 cycles or until progression, unacceptable adverse events or other reason necessitating withdrawal. In case of ongoing clinical benefit a maximum of 5 additional treatment cycles can be given.

[figure not shown]

Figure 6.1:1 Overall study design

For all analyses, statistics will be tabulated by treatment dose group (see [Table 6.1: 1](#)).

Table 6.1: 1 Treatment labels for use in the CTR

Treatment label	Short label
BI 836909, 0.2 µg/d, c.i.v. ^[1]	0.2 µg/d civ
BI 836909, 0.4 µg/d, c.i.v. ^[1]	0.4 µg/d civ
BI 836909, 0.8 µg/d, c.i.v. ^[1]	0.8 µg/d civ
BI 836909, 1.6 µg/d, c.i.v. ^[1]	1.6 µg/d civ
BI 836909, 3.2 µg/d, c.i.v.	3.2 µg/d civ
BI 836909, 6.5 µg/d, c.i.v.	6.5 µg/d civ
BI 836909, 13 µg/d, c.i.v.	13 µg/d civ
BI 836909, 25 µg/d, c.i.v.	25 µg/d civ
BI 836909, 50 µg/d, c.i.v.	50 µg/d civ
BI 836909, 100 µg/d, c.i.v.	100 µg/d civ
BI 836909, 200 µg/d, c.i.v.	200 µg/d civ
BI 836909, 400 µg/d, c.i.v.	400 µg/d civ
BI 836909, 800 µg/d, c.i.v. ^[2]	800 µg/d civ

[1] The 1st four treatment label (0.2 – 1.6 µg/d) may be combined into one column for selected displays.

[2] Further doses will be tested in case that MTD could not be confirmed at a dose level of 800 µg/day. Intermediate doses cohorts will be entered if determined by the safety committee, for example, in case that the dose cohort 400 µg/day exceeds MTD (>1 patients out of 6 with DLT) and no DLT is observed on 200 µg/day, 300 µg/day might be considered.

The purpose of the definition below is to describe the different study interval in this trial.

The treatment periods of the study are:

- Screening period:
The screening period starts from the date of informed consent and ends at the date of the first administration of study drug.
- Treatment period:

Treatment period starts from the date of the first administration of study drug and ends at the date of the last administration of study drug.

- Residual effect period:

Residual effect period starts from the date of the last administration of study drug + 1, and ends at the date of the last administration of study drug + 30 days .

- Follow-up period;

The Follow-up period starts from the last administration of study drug + 30 days.

Please see [Table 6.1:2](#) below, for a definition of treatment periods. The purpose of the definitions below is to describe the treatment periods in this trial.

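### Analysing every endpoint by originally assigned dose mislabels Css and later-course DLTs and adverse events once a patient's dose has changed

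*SAP*

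**What the plan says.** SAP section 7 sets one attribution rule for the whole analysis: "patients will be included in the dose cohorts they were originally assigned to". SAP 6.1 adds: "For all analyses, statistics will be tabulated by treatment dose group". Its treatment labels are the planned dose levels. There is no label for dose at onset or dose at sampling.

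The protocol allows dose to change within a patient:

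- **Reduction.** Protocol 4.1.4.3: "a dose reduction to the next lower dose level is allowed if clinically indicated", limited to one step. The same section adds: "In case of dose reductions all future courses will also be at the reduced dose level". Protocol 4.1.4.5 also allows a restart at the next lower level after a pause, kept for later cycles. The CRS table in 4.1.4.1.4 names a specific reduction from 400 to 200 µg/day.
- **Escalation.** Protocol 3.2: "Intra-patient dose escalation is allowed once to the next higher dose within the first 4 above-mentioned dose cohorts up to 1.6µg/d". After a first cycle without DLT, "the patient can be treated at the next higher dose level in subsequent cycles".

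The affected outputs are planned ones. Protocol 7.3.1 says "the number of patients with all DLTs during any treatment course will be analysed", and SAP 7.4 and 7.8.1 repeat this. For Css, protocol 7.3.5 says "if possible, dose proportionality will also be explored descriptively". Protocol 5.2.1 uses later-cycle events that meet the DLT definition to confirm the MTD and to choose the recommended dose.

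**The concern.** Assigned dose and received dose agree at the start of treatment but can part after cycle 1. From then on, a table by assigned cohort answers a different question from the one these outputs serve, namely what happens at a given dose.

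Two outputs matter. All-course DLTs and adverse events help confirm the MTD and select the recommended dose. If a patient is reduced and then has an event, the event is counted at the level above the one being infused. The lower level, a natural candidate for the recommended dose, then looks cleaner than it was. Css against dose is the other output. If no MTD is found, protocol 3.1 rests the recommended dose on PK and pharmacodynamic data, and a dose-proportionality display with the wrong dose on its axis cannot do its job.

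The planned tables would not let a reader undo this. The exposure summary in SAP 7.7 reports time, courses and cycles, not dose given. The table of adverse events leading to dose reduction shows who was reduced, but not the dose at which later events began.

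**Working it through.** There is no stated figure to reproduce: protocol 7.7 bases the sample size on no power calculation, and the analyses are descriptive.

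**Step 1. Size of one dose step.** From the doses in protocol Table 3.1:1, the ratios of neighbouring levels are 2.0 throughout, except 6.5/3.2 = 2.03 and 25/13 = 1.92. One change therefore makes the label wrong by about a factor of two.

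**Step 2. Who can change dose.**

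- Escalation is capped at 1.6 µg/day, so without cohort expansion only the single patients at 0.2, 0.4 and 0.8 µg/day can escalate: three patients.
- Reduction is open at every level above 0.2 µg/day. At 0.2, protocol 4.1.4.4 requires discontinuation instead.
- Levels from 3.2 µg/day upward are not pooled in any display. Pooling of the lowest four is stated for the cycle 1 DLT display (SAP 7.4) and is optional for selected others (SAP 6.1).

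**Step 3. Css after a reduction.** Assume that Css is proportional to dose, that patients at one dose share the same Css, and that k of n patients were reduced by half. Relative to the value at the labelled dose:

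- arithmetic mean = ((n − k) + 0.5k)/n
- geometric mean = 0.5^(k/n)

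| Reduced | Arithmetic | Geometric |
|---|---|---|
| 1 of 6 | 5.5/6 = 0.92 | 0.89 |
| 1 of 3, or 2 of 6 | 2.5/3 = 0.83 | 0.79 |

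For a single-patient cohort after escalation the ratio is 0.4/0.2 = 2.0, which is one patient's value. By dose infused at sampling, every ratio returns to 1.0 under the same assumptions.

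**Step 4. DLTs over all courses.** Suppose the 200 µg/day cohort has 1 DLT in 6 patients, and one patient reduced from 400 to 200 has a DLT in a later course.

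- By assigned dose, the 200 column shows 1/6 = 17% and the later DLT is counted at 400.
- By dose at onset, with patients exposed at that dose as denominator, the 200 column shows 2/7 = 29%.

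The counts in steps 3 and 4 are assumed; no document gives a reduction frequency.

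**Step 5. What cannot be settled.** Protocol Appendix 10.2 schedules concentration samples on days 15, 22 and 29 of courses 2 to 5 as well as in course 1. The visible text does not say which cycle or cycles supply Css.

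**The case against.** The strongest reply is that the decisions that matter are untouched. The MTD is defined on cycle 1 DLTs, for which assigned dose is appropriate. Escalation is decided by a safety committee that sees all available data, including repeated cycles, not by end-of-trial tables. This stands as far as it goes: the primary analysis needs no change. But protocol 5.2.1 also gives later-cycle events a role in confirming the MTD and selecting the recommended dose.

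A second reply is that the SAP section 7 sentence governs table layout and is no PK derivation rule. SAP 6.3 refers PK handling to protocol 7.3.5, SAP 7.5.2 defers derivation to a sponsor standard, part of the PK text is redacted, and the dense profile is in cycle 1. This stands in part: it is not established that post-change samples enter Css. Yet the sentence covers all analyses, and no visible text exempts Css.

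A third reply is that step dosing does little harm. Under protocol 5.2.1.1 the full target dose runs from day 9, so samples on days 15, 22 and 29 are at the assigned dose. That is right; only the day 8 sample of cycle 1 would fall in the lower-dose phase.

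A reader might also infer that the rule makes the higher dose look safer. For events it does not. SAP 7.8.1 counts subjects, and a patient reduced from 400 to 200 µg/day belongs in the 400 denominator either way, having received 400 first. Assigned-dose counting can only add later events to the 400 column. It is the lower level that looks too clean; the higher level looks under-exposed on Css alone.

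**Conclusion.** The rule should be narrowed. Followed literally, it attaches a dose wrong by about a factor of two to events and concentrations after a dose change, and no visible text provides an analysis by dose received. Reduction above 0.2 µg/day is the main route. Escalation reaches about three patients, all at or below 1.6 µg/day, and is minor.

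The size is illustrative. Under linear PK, one reduced patient in a cohort of 6 or 3 puts mean Css at 92% or 83% of the value at the labelled dose (89% or 79% on the geometric scale). In the DLT example the lower level reads 17% instead of 29%. The true effect depends on how many patients change dose and which cycle Css comes from, and the documents give neither.

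They do not support a claim that the MTD is biased, or that the planned Css summary is certainly wrong. Escalation starts after cycle 1, so the cycle 1 table could be touched only by a reduction or step dosing within that cycle.

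**What to change.** Change SAP section 7 in three places:

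1. Limit the assigned-cohort rule to cycle 1 DLTs, demographics and the main by-cohort tables.
2. State that Css and dose proportionality use the dose being infused at sampling, or only samples taken before any dose change, and name the cycle or cycles that supply Css.
3. Add one supplementary table of DLTs and adverse events after cycle 1 by dose received at onset, with patients exposed at that dose as the denominator.

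The cost is SAP wording and one table. Infusion-rate changes, interruptions and sampling times are already recorded in the eCRF (protocol 4.1.4.1.4 and 5.5). The primary MTD analysis stays as it is.

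Protocol 4.1.4.3 also needs reconciling. It says that a DLT leads to permanent discontinuation in the dose-escalation phase, and then allows the cycle to continue at the next lower tier after recovery. Which statement applies determines how many patients change dose, and so how much the added table will show.

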7.1 DEMOGRAPHIC AND OTHER BASELINE CHARACTERISTICS

Only descriptive statistics are planned for this section of the report. Demographic and baseline characteristics collected and to be presented include

- Gender (*Male/Female*)
- Age [*years*]
- Race (as defined in the eCRF)
- Body height [*cm*]
- Body weight [*kg*]
- Body mass index at baseline [*kg/m²*]
- Body surface area at baseline [*m²*]
- Smoking status (as defined in the eCRF)
- Alcohol status (as defined in the eCRF)
- ECOG performance score (*0/1/2*)
- Baseline cytogenetics
- Time since first diagnosis [*months*]
- ISS stage at screening (*I/II/III*)
- Site of tumor manifestation at screening (Bone/CNS/Soft tissue plasmacytoma/Other)
- Number of bony lesions (*None/<10/≥10*)
- Sum of longest diameters of plasmacytomas if present [*mm*]

7.2 CONCOMITANT DISEASES AND MEDICATION

Only descriptive statistics are planned for this section of the report.

7.3 TREATMENT COMPLIANCE

Non-compliance is defined by any patients who are administered study medication less than 14 days in any cycle (excluding those who discontinued per protocol, e.g., due to AE, or PD). Number of non-compliant patients will be summarized by descriptive statistics.

7.4 PRIMARY ENDPOINTS

In order to identify the MTD, the number of patients with DLTs during Cycle 1 at each dose level will be displayed descriptively by dose level with the lowest 4 doses pooled. In addition, the number of patients with DLTs during any treatment course will be analysed.

7.5 SECONDARY ENDPOINTS

7.5.1 Key secondary endpoint

This section is not applicable as no key secondary endpoint has been specified in the protocol.

7.5.2 Other Secondary endpoints

Objective response rate (ORR)

Objective response rate is defined as the percentage of patients achieving a sCR, CR, PR and VGPR as evaluated by the investigator according to the response criteria of the International Myeloma Working Group. The objective response rate will be presented as the proportion of responders, with the exact 95% Clopper-Pearson confidence intervals. The best response (sCR > CR > PR > VGPR) across all assessment will be used and presented.

Duration of response (DOR)

For patients with objective response, the duration of response is calculated from the time of first recorded achievement of a response until documented progression or death. DOR will be summarized descriptively by quartiles if applicable.

Minimal residual disease (MRD) response

MRD response is defined as <1 tumour cell within 10^4 normal cells in bone marrow using FACS analysis. MRD response rate will be calculated as the proportion of patients achieving MRD response with the exact 95% Clopper-Pearson confidence interval.

Duration of MRD response

For patients with MRD response, the duration of MRD response is calculated from the time of first recorded achievement of a MRD response until documented progression or death. Duration of MRD response will be summarized descriptively by quartiles if applicable.

Progression free survival (PFS)

PFS is defined as the time from first treatment with BI 836909 until disease progression or death. For patients who did not have any event (e.g., alive without progression), their PFS will be censored at date of last documented disease assessment. For patients without any events and no disease assessment performed post-baseline, their PFS will be censored at the date of treatment start. PFS will be summarized descriptively by quartiles with 95% confidence interval calculated from Kaplan-Meier estimate.

Pharmacokinetic analyses

The secondary pharmacokinetic endpoints C_{ss} , [REDACTED] will be descriptively explored, [REDACTED]

Refer to CTP Section 5.5.1 for pharmacokinetic parameters to be calculated. The derivation of the parameters will be according to BI's standard operating procedures. Pharmacokinetic analyses of the plasma concentration-time data will be performed using a validated software program (Phoenix Winnonlin, version 6.3). The analysis of standard PK parameters is performed according to BI standards (see "Standards and processes for analyses performed within Clinical Pharmacokinetics/Pharmacodynamics") [2].

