5.1.2.2 Objective response rate

Objective response rate is defined as the percentage of patients achieving a sCR, CR, PR and VGPR and will be evaluated according to the response criteria of the International Myeloma Working Group (IMWG, 2006; [Appendix 10.1](#)).

- Stringent complete response (sCR)
CR as defined below plus normal FLC ratio and absence of clonal cells in bone marrow by immunohistochemistry or immunofluorescence.
- Complete response (CR)
Complete response is defined as negative immunofixation on the serum and urine and disappearance of any soft tissue plasmacytomas and < 5% plasma cells in bone marrow.
- Very good partial response (VGPR)
Serum and urine M-protein detectable by immunofixation but not on electrophoresis or > 90% reduction in serum M-protein plus urine M-protein level < 100 mg/24 h.
- Partial response (PR)
Partial response is defined as a > 50% reduction of serum M-protein and reduction in 24 hours urinary M-protein by >90% or to < 200 mg/24 h.

Proprietary confidential information.

© 2018 Boehringer Ingelheim International GmbH or one or more of its affiliated companies. All rights reserved.

This document may not - in full or in part - be passed on, reproduced, published or otherwise used without prior written permission.

If the serum and urine M-protein are unmeasurable a > 50% decrease in the difference between involved and uninvolved FLC levels is required in place of the M-protein criteria.

If serum and urine M-protein are not measurable, and serum free light assay is also not measurable, a > 50% reduction in plasma cells is required in place of M-protein, provided baseline bone marrow plasma cell percentage was > 30%.

In addition to the above listed criteria, if present at baseline, a > 50% reduction in the size of soft tissue plasmacytomas is also required.

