7.3.2 Secondary endpoint analyses

Objective response rate (patients with sCR, CR, VGPR, or PR), and MRD response rate will be analysed descriptively. Progression free survival (PFS), duration of response (DOR) and duration of MRD response will be analysed using the Kaplan-Meier method. Details of censoring rules will be provided in the statistical analysis plan.

Refer to [Section 7.3.5](#) for the planned analyses of secondary pharmacokinetic endpoints.

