10. APPENDICES

10.1 INTERNATIONAL MYELOMA WORKING GROUP (IMWG) UNIFORM RESPONSE CRITERIA FOR MULTIPLE MYELOMA

| Response | IMWG criteria ¹ |
|----------------------------------|---|
| sCR | CR as defined below plus normal FLC ratio and absence of clonal cells in bone marrow ² by immunohistochemistry or immunofluorescence ³ |
| CR | Negative immunofixation on the serum and urine and disappearance of any soft tissue plasmacytomas and < 5% plasma cells in bone marrow ³ |
| VGPR | Serum and urine M-protein detectable by immunofixation but not on electrophoresis or > 90% reduction in serum M-protein plus urine M-protein level < 100 mg/24 h |
| PR | > 50% reduction of serum M-protein and reduction in 24 hours urinary M-protein by >90% or to < 200 mg/24 h If the serum and urine M-protein are unmeasurable, ⁵ a > 50% decrease in the difference between involved and uninvolved FLC levels is required in place of the M-protein criteria If serum and urine M-protein are not measurable, and serum free light assay is also not measurable, > 50% reduction in plasma cells is required in place of M-protein, provided baseline bone marrow plasma cell percentage was > 30% In addition to the above listed criteria, if present at baseline, a > 50% reduction in the size of soft tissue plasmacytomas is also required |
| SD | Not meeting criteria for CR, VGPR, PR, or progressive disease |
| Progressive disease ⁴ | Increase of > 25% from lowest response value in any one or more of the following: Serum M-component and/or (the absolute increase must be > 0.5 g/dL) ⁵ Urine M-component and/or (the absolute increase must be > 200 mg/24 h) Only in patients without measurable serum and urine M-protein levels; the difference between involved and uninvolved FLC levels. The absolute increase must be > 10 mg/dL Bone marrow plasma cell percentage; the absolute percentage must be > 10% ⁶ Definite development of new bone lesions or soft tissue plasmacytomas or definite increase in the size of existing bone lesions or soft tissue plasmacytomas Development of hypercalcaemia (corrected serum calcium > 11.5 mg/dL or 2.65 mmol/L) that can be attributed solely to the plasma cell proliferative disorder |

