3. INTRODUCTION

As per ICH E9 [1], the purpose of this document is to provide a more technical and detailed elaboration of the principal features of the analysis described in the protocol, and to include detailed procedures for executing the statistical analysis of the primary and secondary variables and other data.

This TSAP assumes familiarity with the Clinical Trial Protocol (CTP), including Protocol Amendments. In particular, the TSAP is based on the planned analysis specification as written in CTP Section 7 “Statistical Methods and Determination of Sample Size”. Therefore, TSAP readers may consult the CTP for more background information on the study, e.g., on study objectives, study design and population, treatments, definition of measurements and variables, planning of sample size, randomization.

SAS[®] Version 9.4 or newer version will be used for all analyses.

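### SAP 7.5.2 ranks PR above VGPR when deriving best response, and gives no estimator or censoring rule for duration of response and duration of MRD response

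*SAP*

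**What the plan says.** **Best response.** SAP 7.5.2, under objective response rate: "The best response (sCR > CR > PR > VGPR) across all assessment will be used and presented".

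Protocol 5.1.2.2 defines the two categories concerned. VGPR can be met by "> 90% reduction in serum M-protein plus urine M-protein level < 100 mg/24 h", or by M-protein that only immunofixation still detects. For PR, "Partial response is defined as a > 50% reduction of serum M-protein", together with a urine condition. Appendix 10.1 repeats both definitions; its PR entry begins "> 50% reduction of serum M-protein and reduction in 24 hours urinary M-protein". Protocol 7.3.2 lists the categories in order of depth: "Objective response rate (patients with sCR, CR, VGPR, or PR), and MRD response rate will be analysed descriptively".

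**Durations.** Protocol 7.3.2 says that "duration of response (DOR) and duration of MRD response will be analysed using the Kaplan-Meier method", alongside PFS, and then: "Details of censoring rules will be provided in the statistical analysis plan".

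For DOR and for duration of MRD response, SAP 7.5.2 gives the start point, the terminating events (progression or death) and a descriptive summary by quartiles where applicable. It names no estimator and no censoring date for either. For PFS the same section gives both: Kaplan-Meier quartiles with a 95% confidence interval, and censoring at the last documented disease assessment, or at treatment start if there is no post-baseline assessment.

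**The concern.** The ranking is a derivation rule. If it is programmed as written, depth of response is understated whenever a patient has both PR and VGPR on record and nothing deeper. PR followed by VGPR is the ordinary path of a deepening response. Anti-tumour activity is a secondary objective, and protocol 2.2 allows preliminary efficacy data to inform the recommended dose if the MTD is not reached.

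The durations have a different problem. The protocol hands the censoring rules to the SAP, and the SAP supplies them for one of three time-to-event endpoints. A reader who sees Kaplan-Meier stated for PFS and quartiles alone for the other two could compute raw quartiles. Those ignore censoring and can make durations look too short. Ongoing responses are expected: protocol 6.2.5.3 provides visits for responders at 3, 6 and 12 months after EOT so that duration of response can be collected.

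**Working it through.** The plan states no figure to reproduce here: no formal test is planned, and the sample size is not based on power. The check is a comparison of texts, with arithmetic for size.

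**1. Ranking.** Applying the SAP order (sCR > CR > PR > VGPR) and the order of depth (sCR > CR > VGPR > PR) to example response paths:

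| Recorded responses | Best response, SAP order | Best response, depth order | Responder? |
|---|---|---|---|
| PR | PR | PR | yes, both |
| VGPR | VGPR | VGPR | yes, both |
| PR, then VGPR | **PR** | **VGPR** | yes, both |
| VGPR, then PR | **PR** | **VGPR** | yes, both |
| PR, VGPR, then CR | CR | CR | yes, both |

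Only patients with both PR and VGPR, and no CR or sCR, change category. Responder status never changes, so the ORR and its Clopper-Pearson interval are unaffected. DOR starts at the first recorded response of any level, so its start is unaffected too.

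SAP 6.1 tabulates by dose group. Protocol 3.2 gives 3 to 6 patients per level from 3.2 µg/day, and protocol 3.1 adds up to 6 at the MTD or recommended dose (6 + 6 = 12). The shift per affected patient is 1/n:

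- n = 3: 1/3 = 33.3 percentage points
- n = 6: 1/6 = 16.7 percentage points
- n = 12: 1/12 = 8.3 percentage points

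**2. Durations, worked cases with three responders** (+ marks an ongoing response):

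| Times (months) | Raw median, events only | Raw median, ongoing counted as ended | Kaplan-Meier |
|---|---|---|---|
| 4, 10+, 15+ | 4 | 10 | S = 2/3 after month 4 and never reaches 0.5: median not reached |
| 4, 8, 15+ | (4 + 8)/2 = 6 | 8 | S = 2/3, then 2/3 × 1/2 = 1/3 at month 8: median 8 |

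So raw summaries can mislead, but counting the ongoing response as ended does no harm in the second case.

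**3. Durations, simulation (illustration only).** The assumptions are not in the documents: 3 responders per group, exponential DOR with true median 6, 12 or 24 months, follow-up uniform on 3–18 months (1–12 months in brackets), 8,000 groups per setting. Groups with no event are left out of the events-only row.

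| Summary over groups | True median 6 | 12 | 24 |
|---|---|---|---|
| Typical events-only median (months) | 3.7 (2.8) | 4.7 (3.1) | 5.0 (3.4) |
| Typical median, ongoing counted as ended (months) | 4.9 (3.6) | 6.9 (4.7) | 8.4 (5.5) |
| Kaplan-Meier median not reached (% of groups) | 20 (34) | 45 (60) | 69 (78) |
| Counted-as-ended median equals full-follow-up median, among groups with an ongoing response (%) | 43 (27) | 24 (13) | 10 (5) |

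Re-running moves these figures by no more than about 0.2 month or 1 percentage point. In groups this small, the main gain from Kaplan-Meier is an honest statement that the median was not reached, with the number censored.

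**The case against.** *The ranking is a copying slip.* Protocol 5.1.1 and 5.1.2.2 list the responses with PR before VGPR, and the SAP probably put inequality signs between the items of that list. The definitions leave no doubt about depth, and best-response category is not itself a listed secondary endpoint. The likely origin is granted. But those protocol lists only name which responses count, whereas the SAP sentence is an explicit order for derivation and display, and it is wrong as it stands.

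*Kaplan-Meier is already in the plan.* Protocol 7.3.2 and the synopsis both specify it, and SAP section 3 states that "the TSAP is based on the planned analysis specification as written in CTP Section 7". The PFS paragraph also speaks of quartiles and means Kaplan-Meier quartiles. This carries weight: Kaplan-Meier may well be intended, and the raw-quartile results above apply only on the other reading. It does not supply a censoring date, because the protocol gives none.

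*Some SAP text is not public.* Sections 6.4, 7.6 and 9 are absent from the released text, so a general censoring convention there cannot be ruled out. However, the 7.5.2 text on these two durations is complete and refers to no such rule.

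*The PFS rule is equally silent on new anti-cancer therapy.* True. The gap covers all three endpoints. For responders it is narrowed because the extended follow-up visits appear meant to stop at new treatment.

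*The simulated follow-up is invented.* Also true. Ten cycles run 9 × 6 + 4 = 58 weeks, about 13 months; with visits to 12 months after EOT, follow-up could reach about 25 months from first dose. Longer follow-up would mean less censoring than assumed.

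**Conclusion.** Both parts hold. The ranking conflicts with the protocol's own definitions and would misclassify every patient with PR and VGPR but no CR or sCR, at 33.3, 16.7 or 8.3 percentage points each in groups of 3, 6 or 12. How many patients that would be cannot be told from the documents. ORR, its interval and the start of DOR are untouched.

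For DOR and duration of MRD response, the released SAP text omits the censoring rule that the protocol assigned to it and does not restate the estimator. The consequence depends on the reading. Raw quartiles would depart from protocol 7.3.2 and could shorten reported durations. With Kaplan-Meier, the censoring date would be settled only at analysis. The text conflict is certain; the simulated sizes rest on assumed distributions and follow-up.

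No test, DLT count or MTD decision is affected. This should be fixed because the best-response and duration tables would otherwise be wrong or undefined, but it does not threaten the trial's primary purpose.

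**What to change.** In SAP 7.5.2:

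1. Change the best-response order to sCR > CR > VGPR > PR.
2. State that DOR and duration of MRD response are summarised by Kaplan-Meier quartiles, with event-free patients censored at the last documented disease assessment, as for PFS.
3. State how the start of new anti-cancer therapy is handled for both durations, and preferably for PFS at the same time so that the three endpoints agree.
4. Report, per dose group, the number of events, the number censored, and not reached where that applies.

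The cost is one line for the ranking, two or three sentences for the durations, and standard programming. No new data are needed. The change should be made before programming, so that the censoring rule is not chosen after it is known which responses are ongoing.
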